5.1 Part A

Single-ascending oral doses of either LY3478045 or placebo will be administered in up to 5 cohorts. Each cohort will consist of 8 subjects. Cohort 5 is an optional cohort that may be assessed based on the available safety and PK data from the previous cohorts. In each cohort, 6 subjects will be randomized to receive LY3478045 and 2 subjects to receive placebo.

A sentinel dosing strategy will be utilized for Cohorts 3, 4, and 5. Two subjects (1 LY3478045 and 1 placebo) in each cohort will receive a sentinel dose on the same day. After at least 48 hours after dose, the remaining subjects in each cohort may be dosed based on the available safety data.

[figure not shown]

Figure GZKA.1 Illustration of study design for Part A

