9.4 Pharmacodynamic Assessment

9.4.1 CCI █

Plasma concentrations of CCI █ will be listed and summarized by part and treatment, using standard descriptive statistics. Parameters, including predose observed drug concentration ($C_{predose}$), C_{max} , t_{max} , $AUC(0-t_{last})$, and $AUC(0-24)$, will be summarized using descriptive statistics.

In addition, a comparison between log-transformed $C_{predose}$ and C_{max} of CCI █ will be produced using a linear mixed effects model with treatment, concentration phase, and subject as a random effect, where the variable concentration phase will be a variable which indicates whether the concentration value is predose ($C_{predose}$) or postdose (C_{max}). The difference between postdose and predose will be calculated for each treatment and will be back-transformed to present the ratios of geometric least squares means and the corresponding 95% CIs.

The following comparisons will be calculated from the model (including associated p-values):

- Postdose versus predose for each treatment group and placebo
- At the postdose timepoint, comparisons between each treatment group and placebo

For Part A, the data will be those samples collected from the Day 1 timepoint. For the Part B analysis, an additional fixed effect for day will be added to the model so that comparisons can be performed for each day. For all cohorts in Part B, the data collected from the Day 1 and Day 7 samples will be used. This will be a repeated measures model with an unstructured covariance structure and a compound symmetric structure will be used if the model fails to converge.

Example SAS code for the analysis (Part A):

```
proc mixed data=xxxx;
  class trtmnt concphase subject;
  model conc = trtmnt concphase / ddfm=kr;
  random subject;
  lsmeans trtmnt / pdiff cl alpha=0.05;
  lsmeans concphase / pdiff cl alpha=0.05;
  ods output lsmeans=lsmeans diffs=diffs;
```

run;

Example SAS code for the analysis (Part B):

```
proc mixed data=xxxx;
class treatment day subject;
model logpk = treatment day treatment*day /residual ddfm=kr;
repeated day / subject=subject type=UN;
lsmeans treatment*day / cl pdiff alpha=0.05;
ods output lsmeans=lsm diffs=estims;
run;
```

Plasma concentrations of CCI will also be plotted against dose. The plot will be produced separately by dose level and repeated to include all dose levels on one plot.

Additional analysis may be performed, if warranted, upon review of the data.

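### SAP 9.4.1 compares postdose Cmax of the redacted analyte with placebo without adjusting for each subject's own predose value, and so gives up precision that the collected data could supply

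*SAP*

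**What the plan says.** SAP 9.4.1 analyses log-transformed predose concentration and Cmax together as responses, in a "linear mixed effects model with treatment, concentration phase, and subject as a random effect". It lists two kinds of comparison, both with p-values. One is within group: "Postdose versus predose for each treatment group and placebo". The other is against placebo: "At the postdose timepoint, comparisons between each treatment group and placebo". Results are "back-transformed to present the ratios of geometric least squares means and the corresponding 95% CIs". For Part B a day effect is added, and in all cohorts "the data collected from the Day 1 and Day 7 samples will be used".

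The Part A example code is "model conc = trtmnt concphase / ddfm=kr" with a random subject effect, and has no treatment-by-phase term. The Part B code is "model logpk = treatment day treatment*day /residual ddfm=kr", with neither a phase term nor a baseline term.

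Elsewhere the SAP does adjust for baseline. Section 9.3.1 fits the log Day -2 value as a covariate in the interaction analysis. Section 9.4.2 fits baseline as a covariate when change from baseline is the response.

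**The concern.** The two comparisons control for different things. The within-group one uses each subject's baseline but has no placebo control. The between-group one has the placebo control but uses no baseline. Only the second isolates a drug effect, and it rests on very small groups. SAP 5.1 gives the allocation: "In each cohort, 6 subjects will be randomized to receive LY3478045 and 2 subjects to receive placebo". Between-subject spread therefore sets the width of the interval. A stable between-subject component in the analyte would appear in the predose sample, which is already collected on Day 1, and could be removed.

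At stake is how this exploratory biomarker is read. A real change could be missed, or a baseline difference in the realised sample could be taken for a drug effect. The primary safety objective is not affected.

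**Working it through.** **Inputs.**
- The SAP states no power, SD, correlation or target effect for this analyte (SAP 7), so there is no plan figure to reproduce.
- Part A: 6 per dose against 10 placebo if all five cohorts run and placebo is pooled, or 8 placebo without optional Cohort 5 (SAP 5.1).
- Part B: 6 active and 2 placebo in each of four cohorts, with two placebo labels (SAP 5.2 and 6). That is 6 against 4 within a label.
- Assumed: between-subject CV 40% (30% as an alternative), rho from 0 to 0.85, true ratio 1.5.

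**1. What the contrast estimates.** I computed the generalised least squares weights for 6 against 10 with a random subject intercept and complete data. With a treatment-by-phase term, the postdose contrast puts weight 0 on predose and 1 on postdose at every rho tried from 0.3 to 0.9. Its SE is sqrt(1/6 + 1/10) = 0.516 SD. Including predose as a second response row therefore does not adjust the contrast. (The additive Part A code gives weights 0.5 and 0.5, so it averages the predose and postdose differences and does not produce the listed contrast. That is a separate defect.)

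**2. Precision.** On the log scale s = sqrt(ln(1 + CV^2)) = sqrt(ln 1.16) = 0.385. The unadjusted SE for 6 against 10 is 0.385 x 0.516 = 0.199. The adjusted SE is that times sqrt(1 - rho^2). The 95% half-width is the factor exp(t x SE). For 6 against 10, t is 2.032 on 34 df unadjusted and 2.035 on 33 df adjusted; for 6 against 8 the df are 27 and 26. Power is from the noncentral t for ln 1.5.

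| rho | SE ratio | 6 v 10: half-width factor, power | 6 v 8: half-width factor, power |
|---|---|---|---|
| unadjusted | 1 | 1.50, 50.8% | 1.53, 46.8% |
| 0.3 | 0.95 | 1.47, 54.5% | 1.50, 50.3% |
| 0.5 | 0.87 | 1.42, 62.7% | 1.45, 58.2% |
| 0.7 | 0.71 | 1.34, 79.1% | 1.36, 74.8% |
| 0.85 | 0.53 | 1.24, 96.4% | 1.25, 94.5% |

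At CV 30% and 6 against 10, power goes from 74% to 78%, 85%, 95% and over 99%. The SE ratios do not depend on the CV.

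The formula leaves out the small cost of estimating the slope. In simulations of 6,000 runs per setting (SD 0.4, 6 against 10), the log half-width went from about 0.42 unadjusted to 0.403, 0.367 and 0.302 at rho 0.3, 0.5 and 0.7. At rho 0 it rose slightly, from 0.416 to 0.423.

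**3. Error rate and chance imbalance.** With no drug effect, the same simulations rejected in 4.6% to 5.3% of runs unadjusted and 4.3% to 5.2% adjusted. A one-SE chance imbalance at CV 40% is a ratio of exp(0.199) = 1.22. In runs at rho 0.7 where predose imbalance exceeded one SE (mean 0.318 log units), the unadjusted contrast averaged 0.219 with no drug effect, close to 0.7 x 0.318 = 0.223. The adjusted contrast averaged about 0.

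**4. A systematic difference from pooled placebo.** For illustration I assumed a persistent 1.25-fold difference (0.223 log units) at rho 0.7, in the Part A layout. False positives were 18.6% unadjusted and 7.0% adjusted. The adjusted estimate still carried 0.066, about 0.3 x 0.223. The covariate therefore reduces such a difference without removing it.

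**5. Part B placebo and baseline.** The row label in the schedules is redacted, so I take the redacted multi-sample row covering Days 1 and 7 to be this analyte. Protocol 2.3 gives atorvastatin 4 hours after the study dose on Day 7 in Cohorts 2 and 4, and that row runs from predose to 16 hours. The later Day 7 samples in those cohorts thus follow atorvastatin, and those in Cohorts 1 and 3 do not. Day 7 predose is on treatment. Day 1 predose is before LY3478045 or placebo, but in Cohorts 2 and 4 it follows atorvastatin on Day -2. The same row shows a Day -2 profile in those cohorts. Keeping the placebo labels apart gives an SE factor of sqrt(1/6 + 1/4) = 0.645 SD, against sqrt(1/6 + 1/8) = 0.540 SD if all eight are pooled.

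**The case against.** The best defence is that randomisation already makes the unadjusted contrast unbiased with a sound error rate, and that the gain is hypothetical because the documents give no correlation. Both parts stand. At rho 0.3 the SE falls by only 5%, and at 0 there is nothing to gain.

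The consistency argument is also limited. SAP 9.4.2 analyses absolute values without baseline as well, and the fructose models in 9.4.3 have no baseline term. SAP 9.3.1 is the closer precedent.

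The within-group change is reported for placebo too, so a reader could set each dose's change beside the placebo change. No placebo-corrected change is listed as a contrast, however. A change score beats the raw postdose contrast only if rho exceeds 0.5, whereas a covariate helps at any rho clearly above 0.

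The example code needs repair before either listed comparison can be produced as described. That is true, but adding the missing interaction leaves the placebo contrast unadjusted, so this point survives the repair.

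A reader might also infer that the SAP must name one deciding contrast and drop the within-group p-values. The documents do not support that as a requirement. The pharmacodynamic objective is exploratory, protocol 10.3.3.1 makes the fructose tolerance test the primary pharmacodynamic evaluation, protocol 10.3.3.2 plans unadjusted p-values, and the text on this analyte's purpose is redacted.

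**Conclusion.** The point holds as a loss of precision and a lack of protection against imbalance in the realised sample. The SE multiplier sqrt(1 - rho^2) is general, apart from the small cost of estimating the slope. The interval and power figures rest on the assumed CV, correlation and effect, and the 6-against-10 column also needs optional Cohort 5.

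Two stronger readings are tempting and are not supported. The first is that the planned contrast is biased or has an inflated error rate. Within a randomised comparison it is neither. The second is that female-only cohorts distort the comparisons quantified above. That rule is a footnote to the Part B schedules (protocol 2.2 and 2.3), and protocol 7.4.1 has both sexes dosed in Part A, whereas every power and interval figure above is for Part A. In Part B the route is plausible when placebo is pooled across cohorts, but the documents give nothing from which to size it.

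The change is worth making because it is nearly free. It is not a condition for the trial's conclusions on safety.

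**What to change.** In SAP 9.4.1, estimate the LY3478045/placebo ratio of geometric mean Cmax from a model of log Cmax on treatment, with log pre-treatment predose as a covariate. In Part B add day and treatment-by-day. State that the covariate is the Day 1 predose value on both analysed days, not the Day 7 predose value.

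For Part B on Day 7, compare Cohorts 2 and 4 with placebo plus atorvastatin and Cohorts 1 and 3 with placebo alone, in line with the labels in SAP 6, or include an atorvastatin term. Do not pool all placebo subjects without adjustment. Note that Day 1 predose in Cohorts 2 and 4 follows atorvastatin, and say whether the Day -2 profile will serve as a sensitivity baseline there.

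The cost is SAP wording, one covariate in the code and one degree of freedom. Keeping the placebo labels apart on Day 7 costs some precision (0.645 against 0.540 SD), which an atorvastatin term could partly recover. No new data are needed. Naming a single deciding contrast, or making the within-group ratios descriptive, is optional.

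### SAP 9.4.1: the Part B example code indexes the covariance by day only and omits concentration phase, and the Part A code has main effects only, so neither delivers the stated comparisons

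*SAP*

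**What the plan says.** SAP 9.4.1 sets up a mixed model for log-transformed predose concentration and log-transformed Cmax of the redacted analyte. The factors are treatment and a concentration-phase variable that "indicates whether the concentration value is predose" or postdose, with subject as a random effect. Results are to be back-transformed to "ratios of geometric least squares means and the corresponding 95% CIs". Two comparisons are required: postdose against predose within each treatment group and placebo, and each treatment group against placebo at the postdose time.

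For Part B, a day effect is added, and "For all cohorts in Part B, the data collected from the Day 1 and Day 7 samples will be used". The covariance is described as "a repeated measures model with an unstructured covariance structure and a compound symmetric structure will be used if the model fails to converge". The prose does not say what indexes that structure. The Part B example code does: "repeated day / subject=subject type=UN". Its fixed effects are treatment, day and their interaction, with no phase variable in CLASS or MODEL, and its means come from "lsmeans treatment*day / cl pdiff alpha=0.05".

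The Part A example code reads "model conc = trtmnt concphase / ddfm=kr", with least-squares means for treatment and for phase separately.

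**The concern.** The text and the code describe different data. The text puts predose and Cmax from two days into one model. The Part B code has no place for phase, either in the means or in the covariance. A programmer following both would reach a model that cannot be fitted, and the stated fallback would not rescue it. The model would then have to be reinvented, possibly after data are seen.

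Part A has a related gap. Without a treatment-by-phase interaction, the model forces one postdose/predose ratio on every treatment group, although the SAP asks for that ratio group by group.

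**Working it through.** **Plan figure.** The SAP gives no variance, effect size or power for this analysis. The one numeric check is that 95% intervals match alpha = 0.05 in the code, which they do.

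**Rows per subject.** 2 phases x 2 days = 4. SAP 9.3 derives both predose concentration and Cmax for the PD analyte, so all four values are planned.

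**Covariance on the day index.** Order the rows as Day 1 predose, Day 1 Cmax, Day 7 predose, Day 7 Cmax. With covariance indexed by day alone, R = Z G Z', where Z has rows (1,0), (1,0), (0,1), (0,1) and G is 2 x 2. Rows 1 and 2 of R are identical, as are rows 3 and 4.

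- Unstructured, illustrative G = [0.10, 0.06; 0.06, 0.14]: rank 2 of 4, determinant 0.
- Compound symmetric, illustrative G = [0.12, 0.08; 0.08, 0.12]: rank 2 of 4, determinant 0.

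The result does not depend on the values chosen. Two same-day values are given correlation 1, so the likelihood is undefined in both cases.

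**One value per subject-day.** R is then G itself, rank 2 of 2, and the code runs. If the value is Cmax, the treatment-by-day means give the comparison with placebo but not postdose/predose. If it is the predose value, they give neither. A log ratio of the two, which the text does not describe, would give postdose/predose but not the postdose comparison with placebo. No single response gives both.

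**Stacked data with the code's own fixed effects.** Suppose the repeated effect were dropped so that the model runs. A treatment-by-day contrast then averages the two phases. A true postdose ratio of 2.0 with no predose difference is estimated as sqrt(2.0 x 1.0) = 1.41, and a ratio of 3.0 as 1.73. The Part A treatment contrast averages over phase in the same way.

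**Compound symmetry over all four values, full fixed effects.** The SAP does not specify this, but it is a likely repair. With equal variances, the fitted residual variance tends to (1 - mean pairwise correlation) x variance. Assume same-day correlation 0.8 and cross-day 0.5:

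- Mean correlation = (2 x 0.8 + 4 x 0.5)/6 = 0.6, so the residual fraction is 0.4.
- Same-day difference: true fraction 1 - 0.8 = 0.2; SE ratio sqrt(0.4/0.2) = 1.41, so intervals are too wide.
- Cross-day difference: true fraction 1 - 0.5 = 0.5; SE ratio sqrt(0.4/0.5) = 0.89, so intervals are too narrow.

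Coverage of nominal 95% intervals was simulated with 10,000 runs per case, 8 pooled placebo and 4 x 6 active subjects, and Satterthwaite degrees of freedom. All SDs and correlations are assumptions (log-scale SD 0.3 unless varied).

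| Assumed truth | Post vs pre | Active vs placebo, postdose | Day 7 vs Day 1, postdose |
|---|---|---|---|
| Equal SD, all correlations 0.6 | 94.9% | 95.1% | 94.9% |
| Same-day 0.8, others 0.5 | 99.4% | 95.4% | 91.5% |
| Same-phase 0.8, others 0.5 | 92.0% | 94.6% | 99.1% |
| Postdose SD 1.5x predose, all 0.6 | 94.8% | 90.3% | 91.5% |
| Postdose SD 2x predose, all 0.6 | 93.7% | 88.0% | 90.9% |
| SD doubled at Day 7 postdose only, all 0.6 | 88.2% | 80.8% | 88.3% |

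A repeat of rows 1, 2, 4 and 5 with 40,000 runs agreed within 1 percentage point. In row 2 the Day 7 versus Day 1 figure was 92.2%, so about 92% is a fair reading.

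**The case against.** The code is labelled as an example. The prose names no covariance index, so read alone it permits the 4 x 4 unstructured matrix that is needed. The singularity appears only when the data in the prose meet the REPEATED line in the code. The analysis is exploratory, and no primary or secondary objective rests on it. All of that is correct and limits the weight of the point. It does not remove it: the example is the only place where the index is stated, and neither the prose nor the code contains the treatment-by-phase term that the listed comparisons need.

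Two stronger readings are tempting, and the documents do not support them.

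- A reader might infer that the compound-symmetric fallback produces wrong intervals. On the day index it produces none, because it is singular too. Intervals arise only if compound symmetry is placed over all four values, which the SAP does not say. They then have close to nominal coverage when all variances and correlations are equal.
- A reader might infer from the name conc that Part A is analysed on the raw scale. The prose specifies log-transformed values back-transformed to ratios, and the data set in the code is a placeholder. The other ratio analyses in the SAP use response names that contain log, so this is a mismatch to correct. It does not show that a raw-scale analysis is planned.

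**Conclusion.** The point holds as a specification error in an exploratory analysis. On the four values per subject that the text describes, the Part B code cannot be fitted under either the unstructured form or the fallback (rank 2 of 4). This is algebra and needs no assumption beyond stacking the values. With one value per subject-day, the code fits but does not supply both required comparisons. The Part A code cannot give the per-treatment contrasts, and its response name disagrees with the text.

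The size of any interval error depends on how the model is repaired. Plain compound symmetry over the four values keeps about 95% coverage if variances and correlations are all equal. Under the assumed 0.8 same-day and 0.5 cross-day correlations, coverage is about 99% for postdose/predose and about 92% for Day 7 versus Day 1. The analyte is redacted and the documents give no correlations, so these figures are illustrative. The change should be made before analysis. It does not affect the safety or LY3478045 PK objectives.

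**What to change.** **Part B.**
- Add `concphase` to CLASS, use `treatment|day|concphase` in MODEL, and take LSMEANS of `treatment*day*concphase`.
- Replace the repeated line with `repeated day*concphase / subject=subject type=UN`, and state that no additional random subject effect is fitted.
- Define the fallback in full: random subject plus random subject-by-day, with separate predose and postdose residual variances if estimable. Do not use plain compound symmetry over the four values.

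**Part A.**
- Add `trtmnt*concphase` to MODEL and take its LSMEANS.
- Name the log-transformed concentration as the response.

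**Prose.** State the interactions and the day-by-phase covariance index, so that text and code agree.

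**Cost.** SAP wording and several lines of code in both models; no new data. The unstructured matrix has 4 x 5/2 = 10 covariance parameters for up to 4 x 8 = 32 subjects. That is feasible, but small enough for the fallback to matter.

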9.4.2 Biomarkers

Biomarkers including fasting insulin, adiponectin, low- and high-density lipoproteins, cholesterol, and triglycerides will be listed and summarized by Part, treatment and timepoint.

Untransformed absolute values as well as change from baseline in each parameter will be analyzed, separately for each Part, using a mixed-model repeated-measure model to evaluate treatment effects as well as treatment comparisons. The model will include treatment, timepoint and treatment-by-day interaction as fixed effects, subject as a random effect and baseline as a covariate (for the change from baseline analysis). An unstructured covariance structure will be used and a compound symmetric structure will be used if the model fails to converge. The analysis will compare each dose of LY3478045 against placebo at each day. Least squares means as well as 90% CIs will be reported.

Example of SAS code as follows.

```
proc mixed data=xxxx;
class treatment timepoint subject;
model result = treatment timepoint treatment*timepoint /residual ddfm=kr;
repeated timepoint / subject=subject type=UN;
lsmeans treatment*timepoint / cl pdiff alpha=0.1;
ods output lsmeans=lsm diffs=estims;
run;
```

The above code will include baseline as a covariate for the change from baseline parameters.

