9.4.3 Fructose Tolerance Test

Fructose Tolerance Test (FTT): Three meals (breakfast, lunch, and dinner) will be served at approximately 20 minutes, 6 hours, and 12 hours after dose with low fructose content. A beverage containing mixture of fructose CCI CCI in approximately 300 to 500 mL of non-caloric solution) will be served with each of the

3 meals on Day 1 in Part A, and Days 1 and 14 in Part B. AUC(0-24), AUC(0-6), AUC(6-12), and AUC(12-24) for FTT will be calculated using trapezoid methods.

In Part A, the AUC(0-24), AUC(0-6), AUC(6-12), and AUC(12-24) from the FTT will be log-transformed prior to analysis. A linear fixed effects model will be fitted to the fructose data. The model will include Treatment as a fixed effect. The difference in least-square treatment means (LY3478045 – Placebo) along with the 90% CIs will be back-transformed to produce the ratio of geometric means and the CIs comparing LY3478045 to Placebo.

Example of SAS code as follows:

```
proc mixed data=xxx;
class treatment;
model log_AUC = treatment /residual ddfm=kr;
lsmeans treatment / cl pdiff alpha=0.1;
ods output lsmeans=lsm diff=estims;
run;
```

In Part B, the AUC(0-24), AUC(0-6), AUC(6-12), and AUC(12-24) from the FTT will be log-transformed prior to analysis. A linear mixed effects model will be fitted to the data. The model will include treatment, day and the interaction between treatment and day as fixed effects and subject as a random effect. The difference in least-square treatment means (LY3478045 – Placebo) along with the 90% CIs will be back-transformed to produce the ratio of geometric means and the CIs comparing LY3478045 to Placebo. Similar comparisons will be calculated between Day 14 and Day 1 for LY3478045.

Example of SAS code as follows:

```
proc mixed data=xxx;
class treatment day subject;
model log_AUC = treatment|day /residual ddfm=kr;
random subject;
lsmeans treatment*day / cl pdiff alpha=0.1;
ods output lsmeans=lsm diff=estims;
run;
```

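### SAP 9.4.1: the Part A model has no treatment-by-phase interaction, so it cannot give the two comparisons the section lists, and the Part B code drops the phase term its text keeps

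*SAP*

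**What the plan says.** SAP 9.4.1 compares log-transformed Cpredose with log-transformed Cmax of the redacted analyte. Of the within-arm comparison it says: "The difference between postdose and predose will be calculated for each treatment". It then lists two sets of contrasts to be taken from the model, with p-values. The first is postdose against predose for each treatment group and for placebo. The second is: "At the postdose timepoint, comparisons between each treatment group and placebo". Ratios of geometric least squares means with 95% confidence intervals are to be reported.

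For Part A the text names treatment, concentration phase and a random subject effect. The example code agrees: "model conc = trtmnt concphase / ddfm=kr". Its LSMEANS statements cover each factor alone, for instance "lsmeans concphase / pdiff cl alpha=0.05".

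For Part B the text says "an additional fixed effect for day will be added to the model so that comparisons can be performed for each day". The code is "model logpk = treatment day treatment*day /residual ddfm=kr". Phase is absent from CLASS, MODEL and LSMEANS, and REPEATED is indexed by day only.

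The next two sections state their interactions in words. Section 9.4.2 has "treatment-by-day interaction as fixed effects", and Section 9.4.3 has "The model will include treatment, day and the interaction between treatment and day as fixed effects".

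**The concern.** Both listed comparisons are simple effects: phase within arm, and arm within phase. An additive model assumes that the first is the same in every arm and the second is the same at both phases. That assumes away the drug effect the analysis is meant to measure. An ESTIMATE statement would return a number for each contrast, but a constrained one.

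In Part A, three things follow:
- A rise in the LY3478045 arms would be shown partly as a rise on placebo.
- The drug/placebo ratio would be pulled towards 1.
- The modelled postdose/predose ratio could not vary with dose.

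The ratios, intervals and p-values would then disagree with the descriptive summaries beside them.

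In Part B, text and code cannot both be followed. If only Cmax rows are entered, the code gives drug versus placebo by day but no postdose/predose comparison. If predose and Cmax rows are both entered, phase is ignored and each subject has two records at each level of the REPEATED effect.

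**Working it through.** **Inputs from the documents.** SAP 5.1 gives up to five Part A cohorts of 6 LY3478045 and 2 placebo subjects. SAP Section 6 treats placebo as one Part A treatment, so there are 10 placebo subjects, five doses of 6, and 40 subjects with two values each. The plan states no variance, expected effect or power for this analysis.

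**Parameters.** Six treatments by two phases make 12 cell means. The additive model has 1 + 5 + 1 = 7 fixed parameters. With the interaction it has 12.

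**Drug versus placebo.** With one value per phase per subject, the additive treatment contrast is the mean of the predose and postdose contrasts. If predose levels are equal and the true postdose ratio is R, the log estimate is (0 + log R)/2, so the reported ratio is √R:

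| True ratio | Additive model |
|---|---|
| 1.5 | 1.22 |
| 2.0 | 1.41 |
| 3.0 | 1.73 |

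**Postdose versus predose.** The additive phase ratio is the geometric mean of all 40 subjects' ratios, and it is assigned to every arm. With a true placebo ratio of 1.00:
- Only the top dose doubles the analyte: 2^(6/40) = 1.11.
- All five doses double it: 2^(30/40) = 1.68.

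**Simulation.** Assumed true ratios were 1, 1, 1, 1.2 and 2 for the five doses and 1 for placebo. Assumed log-scale SDs were 0.10 or 0.20 within subject and 0.2 or 0.4 between subjects. There were 4000 trials per setting, with a single postdose value rather than a maximum:
- Additive 95% CI for the top dose versus placebo contains 2.0: 13% to 68% of trials.
- Additive model declares placebo increased: 60% (within-subject SD 0.20) to 96% (SD 0.10).
- With the interaction, coverage is about 95% for both the postdose contrast and the placebo-adjusted ratio.

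**Cmax as a maximum.** Cmax is the largest of several samples set against one predose sample, so it exceeds Cpredose even with no drug effect. If the redacted sampling row in Protocol 2.1 is this analyte, there are 7 postdose samples on Day 1, or 8 with the 24 h sample. The null ratio is exp(SD × √(1 − ρ) × E[max]), where E[max] of standard normals is 1.352 for 7 and 1.424 for 8, and SD is 0.10 to 0.20:
- ρ = 0: 1.14 to 1.31 (7 samples); 1.15 to 1.33 (8).
- ρ = 0.5: 1.10 to 1.21 (7 samples); 1.11 to 1.22 (8).

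This inflation occurs in every arm and largely cancels in a placebo-adjusted ratio.

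**The case against.** The code is labelled as an example, and the section says which comparisons are wanted. Its Part B code contains a treatment-by-day term that its Part B text does not name, so the text is not a complete list of terms. An incomplete specification may be a fairer description than a deliberate exclusion. That is reasonable as to intent, but nothing in the section supplies the missing treatment-by-phase term.

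The interaction alone does not make the within-arm comparison safe. When the simulation uses the maximum of 7 samples, placebo is declared increased in essentially every trial under the additive model, and still in about 94% with the interaction. This stands. The 60% to 96% above therefore isolates the effect of additivity and does not predict what Cmax data would show. It is also why the fix needs the placebo-adjusted ratio, which keeps 95% coverage.

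Part of the error would reveal itself. The phase LSMEANS yield one ratio, while the first comparison needs one row per arm, so a programmer would notice. The drug/placebo contrast carries no such warning.

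The stakes are limited. The analyte is not among the visible primary or secondary endpoints, nor among the PK parameters that Protocol 7.4.1 names for escalation. Descriptive summaries and plots are planned, and further analysis is allowed. This lowers the priority but does not make the specified model answer the stated questions.

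**Conclusion.** The concern holds. As written, Part A gives one postdose/predose ratio for all arms and a drug/placebo contrast averaged over phases; neither is what Section 9.4.1 lists. The Part B code contradicts its text.

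The common-ratio constraint needs no assumption about the data. The square-root attenuation needs only equal predose levels and complete pairs. The values 1.11 and 1.68 depend on which doses have an effect. The coverage and error rates rest on assumed SDs and effects, and the Cmax inflation also rests on an assumed within-day correlation and on the identity of a redacted row. The analysis appears exploratory, so this should be fixed before analysis but does not threaten the primary safety objective.

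**What to change.** **Part A.** In both text and code, model the log-transformed concentration with `trtmnt`, `concphase`, `trtmnt*concphase` and random subject, and request LSMEANS for `trtmnt*concphase`. Rename the response: the code calls it `conc`, while the text says it is log-transformed. Report the placebo-adjusted postdose/predose ratio beside the two listed comparisons.

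**Part B.** Add `concphase` and its interactions with treatment and day to the code, request the matching LSMEANS, and index the covariance by day and phase. The larger covariance matrix may not converge at this sample size, so the compound-symmetric fallback already in the SAP should be restated for it.

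**Cost.** A few lines of text and code, and no new data. Part A within-subject degrees of freedom fall from 40 − 1 = 39 to 40 − 6 = 34 with five cohorts, or from 32 − 1 = 31 to 32 − 5 = 27 with four. With five cohorts and single postdose values, the placebo-adjusted ratio has a 95% CI of about ×/÷ exp(2.03 × SD × √(2 × (1/6 + 1/10))). That is about 1.16 at a within-subject log SD of 0.10 and about 1.34 at 0.20 (simulation averages 1.159 and 1.342).
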